3.4 Study treatment discontinuation and intercurrent event

The concept of intercurrent event (IE) is one of the estimand attributes.

Unless otherwise noted, treatment discontinuation due to any reason will be considered an IE. Since there is no treatment discontinuation date collected, the treatment discontinuation date is defined as:

- Treatment end date + 31 days.

3.5 Protocol deviations

An important protocol deviation (IPD) is defined as a protocol deviation (PD) likely to have a meaningful impact on the study conduct, the primary efficacy outcome, the key safety or the PK outcomes for an individual subject. The IPDs will be identified and classified by the deviation types defined in the appropriate protocol-specific document. All PDs will be reviewed as part of the ongoing data cleaning and data evaluation process and IPD will be identified and documented prior to unblinding to confirm exclusion from Per Protocol Set (PPS) and the Pharmacokinetics Per Protocol Set (PK-PPS).

An IPD will not always necessitate the removal of a subject from the PPS. Depending on the type of PD, the subject may remain in the PPS. The IPD document developed by the clinical study team should clearly state which PD will result in a removal from the PPS.

In addition to IPDs resulting in the exclusion from the PPS, subjects who reduce the dose or dosing frequency of certain medications due to intolerance, AE, side-effects or receive new prohibited medication for AE will be removed from the PPS. While this is not an IPD, as it is allowed per protocol for safety reasons, these subjects will be removed from the PPS as this non-PD could have an effect on the primary efficacy outcome in the same way as flagged IPDs resulting in exclusion from the PPS.

Since the PPS will be used for a supportive analysis of the primary endpoint, which is assessed at Week 16, the exclusion from PPS is limited to the DBP, ie only subjects with IPD (or the non-PD above) observed prior to or at Week 16 (Visit 10) will be excluded from the PPS. Subjects with IPD after Week 16 will not be excluded from the PPS.

A specific category of PD as a consequence of the Coronavirus Disease 2019 (COVID-19) pandemic (called COVID-19 related PD) will be assessed based especially on the information collected on a dedicated electronic case report form (eCRF) page (and other sources).

3.6 Analysis sets

3.6.1 Enrolled Set

The Enrolled Set consists of all subjects who have given informed consent.

Subject dispositions will be summarized on the Enrolled Set.

3.6.2 Randomized Set

The Randomized Set (RS) consists of enrolled subjects that have been randomized.

Demographic tables, primary, secondary (except VdHmTSS) and other efficacy variables will be presented on the RS.

3.6.3 Safety Set

The Safety Set (SS) consists of all subjects who received at least 1 dose of the IMP.

Demographic tables, study treatment compliance, exposure and safety variables will be presented on the SS.

3.6.4 Full Analysis Set

The Full Analysis Set (FAS) consists of all randomized subjects who received at least 1 dose of IMP and have valid measurements of all the components of the primary efficacy variable at Baseline.

Supportive analysis of the primary efficacy variable will be performed in the FAS.

3.6.5 Active Medication Set

The Active Medication Set (AMS) will consist of all subjects who have received at least 1 dose of active IMP (BKZ or ADA). The AMS will cover the analysis of data collected during the Active Medication Periods (AMP), ie:

- The ATP for subjects randomized to placebo,
- The DBP and the ATP for subjects randomized to BKZ or ADA.

The AMS will be used for summaries of safety during the AMP.

The anti-BKZ antibody will also be analyzed on the AMS for subjects receiving BKZ.

In this analysis set, the order of the treatment groups presented in tables from left to right will be:

- BKZ Total (all BKZ treated subjects)
- ADA 40mg Q2W.

For the analysis of the compliance, study medication and time at risk, the order of the treatment groups to be presented in tables from left to right will be:

- Placebo / BKZ 160mg Q4W
- BKZ 160mg Q4W
- BKZ 160mg Q4W Total (all BKZ treated subjects)
- ADA 40mg Q2W.

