In the TFLs, subjects randomized to BKZ 160mg Q4W will be labeled as “BKZ 160mg Q4W”, subjects randomized to ADA 40mg Q2W will be labeled as “ADA 40mg Q2W” and subjects randomized to Placebo will be labeled as “Placebo / BKZ 160mg Q4W” (or “Placebo” when the TFLs report data from the DBP only).

For the ATP, all subjects on BKZ 160mg Q4W (that includes the subjects switching from Placebo at Week 16) will be labeled as “BKZ 160mg Q4W Total” in the TFLs.

Per protocol, visit windows of ± 2 days from the first dose at all visits through Week 16 and ± 3 days after Week 16 are permissible. For the SFU visit, the visit should occur no more than 3 days prior to the scheduled visit date and within 7 days after the scheduled visit date.

For the medical imaging collection date (at Week 16 and 52), the allowed visit window will be extended to ± 14 days around the scheduled visit date.

All by-visit tables will contain nominal (ie scheduled) visits only. Unscheduled visits will not be mapped to scheduled visits except for some assessments that may occur within the above visit window of a scheduled visit. In that case, the assessment will be mapped to the corresponding scheduled visit and will be used for the analysis unless data are present for that scheduled visit. Only data collected/mapped at the scheduled visits will be included in the analysis. The only deviation may concern unscheduled vendor data collected ([Section 10.5](#)).

Assessments collected at unscheduled and repeated visits will only be listed, except in the case of determining treatment-emergent markedly abnormal criteria for laboratory and vital sign parameters where all post-Baseline (scheduled and unscheduled) values will be used.

For by-visit tables summarizing efficacy data, the SFU visit will not be included but SFU efficacy data will be listed. By-visit tables summarizing safety data will however include the SFU visit. For PK, immunological and immunogenicity analyses, SFU data will be part of the data reported in some tables ([Section 9](#)).

A complete set of data listings containing all documented data and all derived data (eg, change from Baseline) will be generated.

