9.2 Immunological (Immunogenicity) analyses

9.2.1 Anti-bimekizumab antibody

The ADAb will be assessed using a 3-tiered assay approach: Screening, confirmatory, and titration assays. Samples confirmed as positive within the confirmatory assay will be further evaluated for the presence of NAb specific to binding of BKZ to IL-17AA, IL-17FF or both.

Screening, confirmatory and titer cut points of the respective assays will be determined by the bioanalytical laboratory. The relevant statistical reports will be provided as part of the bioanalytical reports.

The ADAb samples are analyzed on the SS but are not analyzed when subjects are on a treatment other than BKZ. For subjects who switch from placebo to BKZ, samples are analyzed at Baseline visit (prior to any dosing) and at the visit (Week 16) when the switch to BKZ occurs. The sample at the visit when the switch occurs will act as the Baseline for that treatment group.

The Screening cut point will be used to determine the ADAb status in the test sample as “Positive Screen” (PS) or “Negative Screen” (NS). For samples presenting anti-BKZ antibody levels that are PS, further confirmatory assay will be performed, and the result of which will be reported as either “Positive Immunodepletion” (PI) or “Negative Immunodepletion” (NI).

The ADAb status for each visit will be derived as following:

- Sample values that are either NS or PS and NI will be defined as ADA_b negative
- Sample values that are either NS or PS and NI and where the BKZ concentration exceeds the validated ADA_b assay drug tolerance limit (200 µg/mL) will be defined as inconclusive.
- Sample values that are PS and PI will be defined as ADA_b positive (regardless of availability of a titer value)
- Missing if it does not go into one of the above categories.

PI samples will be titrated, and the ADA_b titer (reciprocal dilution factor including MRD) reported. The PI samples will also be subject to a neutralizing assay to evaluate whether the anti-BKZ antibody neutralizes the target binding of BKZ (IL17A or IL17F or both) in-vitro.

The following rule will be implemented for by-visit ADA_b summaries where applicable:

- From Baseline through Week 24 visit, if the ADA_b sample is collected within ±14 days relative to the visit date at which the drug was administered (or ±14 days from a scheduled visit at which dosing was not performed), the ADA_b result for that sample will be associated with the scheduled visit and summarized accordingly.

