- **Category 4: Pre ADA_b positive – treatment unaffected ADA_b positive:** Includes subjects who are positive at Baseline and are positive at any sampling point post treatment (including SFU) with titer values of the same magnitude as Baseline (ie less than a predefined fold difference from the Baseline value). For the purposes of this study, this is set at an increase of less than the validated Minimum Significant Ratio (MSR) of 2.07-fold from baseline.
- **Category 5: Pre ADA_b positive – treatment boosted ADA_b positive:** Includes subjects who are positive at Baseline and are positive at any sampling point post treatment (including SFU) with increased titer values compared to Baseline (greater than or equal to a predefined fold difference increase from Baseline value which is defined within the validation of the assay). For the purposes of this study, this is set at an increase greater than or equal to the validated Minimum Significant Ratio (MSR) of 2.07-fold from Baseline.

Note: For any subject who is positive at Baseline and positive at a post-Baseline time point, but for whom titers are not available to determine treatment unaffected or treatment boosted status, the subject will be considered as treatment boosted (ie, Category 5), assuming no other samples are available.

- **Category 6: Inconclusive:** Includes subjects who have a positive pre-treatment sample and some post-treatment samples are missing, while other post-treatment samples are ADA_b negative or missing.
- **Category 7: Total treatment-emergent:** Category 2 and 5 combined: Includes subjects who are pre ADA_b negative – treatment emergent ADA_b positive (Category 2) and pre ADA_b positive – treatment boosted ADA_b positive (Category 5).
- **Category 8: Total prevalence of pre-ADA_b positivity:** (Categories 3, 4, 5 and 6 combined): Subjects that are tested ADA_b positive at Baseline.
- **Category 9: Missing:** Includes subjects who have a negative or a missing/inconclusive pre-treatment sample and some post-treatment samples are missing/inconclusive, while other post-treatment samples are ADA_b negative or missing.

For the subjects randomized to placebo group, the Baseline will be the Week 16 pre-dose observation.

All the following analyses will be prepared on the SS on BKZ treated subjects by treatment group (Placebo / BKZ 160mg Q4W and BKZ 160mg Q4W):

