- A summary table displaying the number and percentage of subjects with ADA_b status - positive, negative, total of positive and negative , missing - at each visit (including SFU) and overall will be provided. For the overall summary at any visit, 2 summaries will be presented:

- Including any visit during the treatment period (as defined in [Section 3.1](#)). Thus, this summary will exclude data obtained at the SFU visit and will include data obtained at Baseline. This summary will display the overall ADAb status up to Week 16 (for the BKZ 160 mg Q4W group), and to Week 24 and 52 by treatment group (BKZ 160 mg Q4W, Placebo / BKZ 160 mg Q4W).
- Including any visit during the study. Thus, this summary will include data obtained at both the SFU visit and at Baseline. Subjects who rolled over to the OLE study will not have a SFU visit per study protocol. For these subjects, the ‘overall ADAb status including SFU’ will then be considered as being identical to the ‘overall ADAb status up to Week 52’.

For the overall ADAb status, a subject will be classified as:

- Positive if the subject has at least one positive sample at any time in the treatment period (regardless of having missing /inconclusive data)
- Negative if the subject has all the samples negative or only one missing/inconclusive sample with negative ADAb samples up to the timepoint of interest
- Missing if the subject has missed more than one sample result for ADAb assessment (or have more than one inconclusive sample) and all other available ADAb samples are negative during the period of interest (If there are $\geq 95\%$ of subjects included in the non-missing groups, the missing group will not be displayed on the table).

- The above summary table displaying the number and percentage of subjects in each of the ADAb status (positive, negative, total of positive and negative, missing) will be repeated for the subjects randomized in Japan for Placebo / BKZ 160 mg Q4W and BKZ 160 mg Q4W groups (overall summaries only). The overall summary excluding SFU will be generated for up to Week 16, 24 and 52.
- A summary table displaying the number and percentage of subjects in each of the ADAb status (positive, negative, total of positive and negative, missing) by concomitant medications (use of cDMARDs at entry, use of MTX at entry, use of oral/systemic corticosteroids at entry) will be provided (overall summaries only, including summaries up to Week 16, 24, 52 and SFU).

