Note: For PK and efficacy analyses up to a certain timepoint (Week 16, 24 and 52) by NAb status, only data up to the timepoint of interest will be utilized in deriving the subject's overall NAb status during that period (eg for the ACR50 by NAb up to Week 16, only NAb data from baseline up to Week 16 will be used to derive subject's overall NAb status during the DBP).

- A listing will be produced to summarize the NAb status overall in the study. The listing will be sorted by treatment group (Placebo/ BKZ 160mg Q4W vs. BKZ 160mg Q4W), subject identifier and visit and will summarize the following information for each subject assessed for NAb:
 - Visit
 - Study week
 - Laboratory sampling date and time
 - Time since previous dose (weeks)
 - The corresponding BKZ plasma concentration level at each visit (ug/mL)
 - Anti-BKZ anti-body titer at each visit
 - IL-17AA NAb status and corresponding IL-17AA signal/negative control result
 - IL-17FF NAb status and corresponding IL-17FF signal/negative control result
- A summary table will provide the following overall summary statistics by treatment group (Placebo/ BKZ 160mg Q4W vs. BKZ 160mg Q4W) (based on the total number of randomized subjects):
 - The number and percentage of subjects confirmed as anti-BKZ antibody positive and anti-BKZ antibody negative up to Week 16, 24, 52 (excluding SFU), 52 (including SFU)
 - The number and percentage of subjects who are NAb positive, NAb negative and missing up to Week 16, 24, 52 (excluding SFU) and 52 (including SFU).

The NAb summary tables will be repeated with percentages calculated on a denominator based on the number of ADAb positive subjects during the above periods.

In addition, the following analyses will be performed to assess the impact of NAb status on efficacy variables:

- Two figures (side by side) summarizing efficacy response (ACR50 based on NRI) versus time for each treatment group (Placebo / BKZ 160mg Q4W and BKZ 160mg Q4W) by NAb status (ADA_b negative, NAb positive, ADA_b positive / NAb negative, missing) will be created. If $\geq 95\%$ of subjects are included in the non-missing groups, the missing group will not be displayed in the figure. Separate figures will be presented for data up to Week 16 (for the BKZ 160mg Q4W group), and to Week 24 and 52 by treatment group (BKZ 160mg Q4W vs. Placebo / BKZ 160mg Q4W). The analyses will be repeated for ACR20 and PASI90 (for

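### The overall ADAb/NAb table in SAP 9.2.2 uses all randomized subjects as denominator, while 3.6.5 and 9.2.1 use BKZ-treated subjects, so overall antibody positivity in the Placebo/BKZ column is diluted and printed with two values

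*SAP*

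**What the plan says.** Three places in the SAP fix the population for antibody results.

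- Section 3.6.5 (Active Medication Set): "The anti-BKZ antibody will also be analyzed on the AMS for subjects receiving BKZ".
- Section 9.2.1 (anti-bimekizumab antibody): "All the following analyses will be prepared on the SS on BKZ treated subjects by treatment group", with Placebo/BKZ 160mg Q4W and BKZ 160mg Q4W as the groups.
- Section 9.2.2 (neutralizing antibodies): an overall summary table for the same two groups, "based on the total number of randomized subjects".

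The 9.2.2 table is not limited to neutralizing antibodies. Its first row is "The number and percentage of subjects confirmed as anti-BKZ antibody positive and anti-BKZ antibody negative up to Week 16, 24, 52 (excluding SFU") and also Week 52 including SFU; the second row gives NAb positive, negative and missing for the same periods. Section 9.2.1 already tabulates overall ADAb status: "This summary will display the overall ADAb status up to Week 16 (for the BKZ 160 mg Q4W group"), then up to Weeks 24 and 52 by group, and once more with SFU data included.

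Three further statements bear on who is counted.

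- Section 3.1 attaches the Placebo/BKZ label by randomization ("subjects randomized to Placebo will be labeled as" Placebo / BKZ 160mg Q4W), without requiring that the switch took place.
- Section 9.2.1 on assay of samples: "The ADAb samples are analyzed on the SS but are not analyzed when subjects are on a treatment other than BKZ".
- Section 9.2.1 on the reference sample: "For the subjects randomized to placebo group, the Baseline will be the Week 16 pre-dose observation".

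**The concern.** Read literally, 9.2.2 counts people who were never exposed to BKZ in the denominator of a percentage that describes antibodies to BKZ. A subject randomized to placebo who stops before Week 16 has no BKZ dose, no Week 16 pre-dose reference sample and no later sample on BKZ. That subject cannot enter the numerator but stays in the denominator.

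Two things follow. The same quantity, overall ADAb positivity by group up to a given week, is printed in one report under two rules. And overall NAb positivity in the Placebo/BKZ column is lower than it is among those exposed, or its missing share is larger. Assessing the immunogenicity of BKZ is one of the objectives in Section 2.1.3, and a reader comparing the two BKZ groups would see dilution in essentially one of them.

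**Working it through.** **1. Do the three populations differ?** The AMS (3.6.5) requires at least one dose of BKZ or ADA; restricted to subjects receiving BKZ, it is everyone with at least one BKZ dose. The Safety Set (3.6.3) requires at least one dose of IMP; restricted to BKZ-treated subjects, it is the same people. So 3.6.5 and 9.2.1 differ in label only. The Randomized Set (3.6.2) requires only randomization. Section 9.2.2 is therefore the one that departs.

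**2. Is the same statistic produced twice?**

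| Overall ADAb status | 9.2.1 | 9.2.2 |
|---|---|---|
| Up to Week 16 | BKZ group only | both groups |
| Up to Week 24 | both groups | both groups |
| Up to Week 52, without SFU | both groups | both groups |
| Including SFU | both groups | both groups |
| Denominator | BKZ-treated, SS | randomized |

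The last three periods are reported under both rules. The Week 16 line shows a related mismatch: 9.2.2 asks for it in the Placebo/BKZ group as well, although that group has had no planned BKZ by then and its Week 16 pre-dose sample is its Baseline.

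**3. Can the two denominators differ in practice?** Section 2.3.2.2 provides for subjects withdrawn before Week 16, so in the Placebo/BKZ column a difference is to be expected. In the BKZ column they differ only if a randomized subject is never dosed.

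**4. Size.** The SAP states no antibody rate and no attrition rate, so there is no planned figure to reproduce. The one planned number used is the placebo arm: 840 × 2/6 = 280, as stated in Section 2.3.1.

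Let d be the share of placebo subjects who never receive BKZ and p the ADAb positivity among those who do. The count of positives is p × 280 × (1 − d).

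- 9.2.1 percentage: p × 280 × (1 − d) / [280 × (1 − d)] = p
- 9.2.2 percentage: p × 280 × (1 − d) / 280 = p × (1 − d)
- gap: p × d

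Both d and p are assumptions:

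| Never receive BKZ (of 280) | d | p = 40% prints as | gap (points) | p = 50% prints as | gap (points) |
|---|---|---|---|---|---|
| 8 | 2.9% | 38.9% | 1.1 | 48.6% | 1.4 |
| 14 | 5.0% | 38.0% | 2.0 | 47.5% | 2.5 |
| 22 | 7.9% | 36.9% | 3.1 | 46.1% | 3.9 |

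Over a wider range, d from 2% to 15% and p from 20% to 50%, the gap runs from 0.20 × 0.02 = 0.4 points to 0.50 × 0.15 = 7.5 points. It is zero only if every placebo subject goes on to receive BKZ. The same factor (1 − d) applies to overall NAb positivity.

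**The case against.** The best defence is that the parenthesis in 9.2.2 is loose wording. Section 9.2.1 has already fixed the population, and the next instruction in 9.2.2 repeats the NAb tables on ADAb-positive subjects, so the parenthesis may only be meant to contrast the whole group with that subset. This is plausible, but it does not remove the problem. The SAP defines randomized and treated sets separately, so a programmer following the text would use the randomized count. The repeat gives NAb a conditional denominator that never-treated subjects do not enter; it does not correct the ADAb percentages or NAb positivity among all exposed subjects.

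Other parts of the defence stand. The table is descriptive, no test or decision depends on it, and immunogenicity is listed among the other objectives. The NAb rows include a missing category, where never-treated subjects may be visible instead of being counted as negative; the positive percentage is still divided by too many.

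A reader might also infer more than the document supports:

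- *That treatment-emergent ADAb incidence is understated.* It is not. The nine-category table and the first-occurrence table are specified in 9.2.1 under the BKZ-treated rule. The 9.2.2 rows give overall status for a period, Baseline included.
- *That 3.6.5 and 9.2.1 conflict.* They name different sets but describe the same subjects.
- *That both columns are biased.* In the BKZ column the gap is zero unless a randomized subject was never dosed.

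**Conclusion.** Wrong as written, and minor. The defect is one phrase in Section 9.2.2. Taken literally, it puts never-exposed placebo subjects in the Placebo/BKZ denominator, so overall ADAb positivity up to Week 24, up to Week 52 and including SFU carries two values in the same report, and overall NAb positivity is scaled down by the same factor.

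The direction is certain once any placebo subject fails to switch. The size is not derivable from the SAP: 1.1 to 3.9 percentage points rests on assumed values of about 3% to 8% never switching and 40% to 50% ADAb positivity. No efficacy result and no treatment-emergent ADAb result is touched.

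**What to change.** In Section 9.2.2, change the denominator of the overall ADAb/NAb summary table from all randomized subjects to BKZ-treated subjects in the SS, that is, those with at least one dose of BKZ. Name this same set in Sections 3.6.5 and 9.2.1. Write the BKZ restriction out; the AMS label alone will not do, because that set also contains adalimumab subjects.

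Keep the planned repeat of the NAb tables on ADAb-positive subjects. While editing, align the Week 16 row with 9.2.1 by limiting it to the BKZ 160mg Q4W group, or state what it is meant to show for Placebo/BKZ.

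The cost is one phrase in 9.2.2, matching set names in two other sections, and the table shell. No new data are needed. The printed Placebo/BKZ percentages rise slightly and agree with those in 9.2.1.
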